1. STUDY SYNOPSIS

Provide brief information

Title:	An Online Educational Course for People with MS: A randomised controlled trial of course effectiveness
Short Title:	Online Educational Course RCT
Design:	Randomised controlled trial (RCT)
Study Centres:	The University of Melbourne
Hospital:	None
Study Question:	
This study proposes to conduct a RCT to test the effectiveness of an intervention/product providing information on MS-related lifestyle behaviour in the form of an online course that was developed by researchers from the Neuroepidemiology Unit (NEU) at the University of Melbourne in modifying participant's behaviour and improving health outcomes in people with MS. The control arm consists of an online course providing general MS-related material that was also developed by the NEU.
 
The research question of the study is: Will a Multiple Sclerosis (MS) Online lifestyle modification course that delivers evidence-based lifestyle modification recommendations to people with MS (the intervention) result in sustained lifestyle behaviour change and improved health outcomes post-intervention compared with people undertaking an MS Online standard-care course (the control)?

Study Objectives:	
To quantitatively and qualitatively assess the outcomes of participants enrolled in the MS Online intervention course compared with the MS Online standard-care course in an RCT. In particular, we aim to:
 
 1) To assess the uptake and maintenance of recommended lifestyle modifications in a cohort of people with MS after undertaking an MS Online intervention course compared with people undertaking an MS Online standard-care course. 2) To assess whether people with MS undertaking and adhering to the guidelines of the MS Online intervention course have improved health outcomes of depression, fatigue, disability, and quality of life over the short-term and medium-term compared with people undertaking and adhering to the MS Online standard-care course.

Primary Objectives:	
To determine whether participants adhering to lifestyle modification recommendations outlined in the MS Online intervention course have clinically significant increased health-related quality of life (HRQOL) in both domains of physical and mental health compared with participants following recommendations of the MS Online standard-care course. These outcomes will be examined in the short-term (6 and 12 months) and in the medium-term (2.5 years).
 
That is, we aim to determine whether participants in the Online intervention course following recommended lifestyle modifications have clinically significant and material increases in Physical Health Composite (PHC) and Mental Health Composite (MHC) scores, as derived from the validated tool designed to measure HRQOL in people with MS (MSQOL-54) compared with participants following recommendations of the Online standard-care course.

Secondary Objectives	
To determine whether participants following the lifestyle modification recommendations in the Online MS intervention course have improved depression, anxiety, fatigue, disability and self-efficacy in the short-term and medium-term compared with people following recommendations of the Online MS standard-care course.

Inclusion Criteria:	
Eligible participants must:
 
 1. Be able to read, write, and speak English; 2. Be 18 years old or over; 3. Have a confirmed diagnosis of relapsing-remitting MS by a neurologist preceding recruitment; 4. Be able to access the internet and be able to view sessions.
Exclusion Criteria:	
Exclusion criteria of participants include:
 
 1. Experiencing any serious co-morbid chronic illness or neurological illness/injury other than MS that would threaten regular participation or significantly affect the outcome measures in its own right, such as motor neurone disease or stroke, as determined by the study investigators; 2. Currently participating in another study or self-management program involving modification of lifestyle.
Number of Planned Participants:	
1054 participants, 527 in each arm at 1:1 allocation (intervention and standard-care arm)

Investigational product:	
Not applicable

Safety considerations:	
Participation in the study poses no physical risk to participants as the proposed RCT involves taking part in an Online MS

	
educational course and completing self-reported questionnaires and possibly two semi-structured qualitative interviews.
 
Any potentially psychological risks from participating in the study have been addressed by contingency plans to provide links to Online help resources and the contact details of study team members to provide further information for participants.

Statistical Methods:	
Analysis of outcomes:
 
Characteristics of quality of life (QoL) will be measured by the MSQOL-54, including physical and mental health composite scores and multiple subdomains. Linear regression will be used to determine cross-sectional and prospective relationships with QoL. Characteristics of disability will be assessed using linear regression. Characteristics of dichotomous clinically significant fatigue and depression will be assessed by log-binomial regression. Characteristics of self-efficacy composite scores will be assessed by linear and log-binomial regression for continuous and dichotomised self-efficacy, respectively. All models will be assessed for potential clinical and demographic confounders and appropriate adjustments will be made in analyses.

Subgroups:	Not applicable
Consumer Involvement	
Consumers have been involved in the co-design of the MSOC RCT. A consumer advisory group comprising of 6-8 people with MS in a series of focus groups was involved in the co-design of the MS Online intervention and standard-care course. The devised course was then tested in a feasibility study (MSOC – Feasibility) involving a subgroup of people with MS (n = 31) and the quantitative and qualitative outcomes of the MSOC – Feasibility study were used to co-design the MS Online intervention and standard-care courses in the proposed RCT.

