The proposed study aims to prospectively determine whether an Online MS Lifestyle Modification Course (the intervention arm) can deliver an evidence-based educational intervention that results in behaviour change which is sustained and is translated into improved health outcomes for people

with MS, and whether these effects are superior to the Online standard-care course (the control arm).

In this RCT, we will be comparing two interventions/products that were developed by researchers at the Neuroepidemiology Unit (NEU) at the University of Melbourne:

1. the MS Online intervention course that delivers information on diet, exercise, Vitamin D and omega-3 supplementation and stress relief/meditation
2. the MS Online standard-care course that delivers standard MS-related information that can be obtained through publicly-available Websites.

In people with MS, we aim to compare health outcomes of people enrolled in the intervention (the MS Online intervention course) with the control arm (the MS Online standard-care course) by assessing:

- assess the uptake and maintenance of recommended lifestyle modifications in a cohort of people with MS after undertaking an MS online educational lifestyle course compared with people undertaking an online standard-care course.
- assess whether people with MS undertaking an MS online educational lifestyle intervention course results in improved clinical outcomes and health outcomes of depression, fatigue, disability, and quality of life over the short-term and medium-term compared with people undertaking an online standard-care course.

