- V. Interested participants meeting the study eligibility criteria (Refer to Section 6.2 and 6.3 for eligibility criteria) after completing the eligibility questions will be emailed a participant information form and consent form. Once participants have provided their consent by ticking a box online, participants will be emailed a link to the baseline questionnaire to obtain demographic data and obtain data on lifestyle and outcome measures (Section 4.3, Table 1). Interested participants not meeting the study eligibility criteria will be excluded and notified by email that they were not eligible to participate in the study and thanking them for their interest.
- VI. Participants will be randomised to either the MS Online intervention course or the MS Online standard-care course at a ratio of 1:1 using simple randomisation. Randomisation will occur over a 2-week period after recruitment of eligible participants.
- VII. Participants will undertake the MS Online course (intervention arm or standard-care arm) over a 6-week period. Note, each arm is of comparable length and content-type (video, interviews, images, interactivity), to minimise variability in 'dose' received between intervention and standard-care groups. Both courses will follow a similar structure throughout, limiting differences in how the content of the course is presented.
- VIII. Patient-reported outcomes measures (Section 4.3, Table 1) will be determined after a period of 6 months, 12 months and 2.5 years after the completion of the MS Online course. This will involve participants from the MS Online intervention arm and the MS Online standard-care arm completing validated questionnaires online (following instructions and reminders, if necessary, from study team members). These measures will determine participants adherence to lifestyle recommendations of the Online intervention and standard course with respect to diet, exercise, omega 3 intake, vitamin D intake, meditation and sun exposure (Table 1). Health outcomes related to participant's quality of life, depression, anxiety, fatigue, disability and self-efficacy.
- IX. The primary objective of the study will be assessed at the 12-month and 2.5 year follow-up. That is, Health-related quality of life (HRQOL) calculations for Physical Health Composite

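### The primary objective compares self-selected adherers, other text compares whole arms, and no analysis population is named to say which comparison is primary.

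*Combined protocol and SAP*

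**What the plan says.** **Text that conditions on adherence.** In the Section 1 synopsis, the Primary Objectives entry asks "whether participants adhering to lifestyle modification recommendations outlined in the MS Online intervention course have clinically significant increased health-related quality of life". It takes as comparator standard-care participants who follow their own course's recommendations, and it then restates the same contrast for PHC and MHC. Study objective 2 reads "To assess whether people with MS undertaking and adhering to the guidelines of the MS Online intervention course have improved health outcomes", again against adherers in the other arm. The Secondary Objectives ask whether "participants following the lifestyle modification recommendations in the Online MS intervention course have improved depression, anxiety, fatigue, disability and self-efficacy".

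**Text that compares arms.** The lead study objective is to "assess the outcomes of participants enrolled in the MS Online intervention course compared with the MS Online standard-care course in an RCT". Section 4.3 says "we aim to compare health outcomes of people enrolled in the intervention (the MS Online intervention course) with the control arm". The hypothesis (5.1) concerns people who undertake each course. The primary endpoint definition (5.3) carries no adherence condition. The quantitative analysis paragraph in 6.1 compares people enrolled in each arm, and 9.1 sizes the trial on a 5-point difference between arms. Section 6.1, item IX, states "The primary objective of the study will be assessed at the 12-month and 2.5 year follow-up" and goes on to describe PHC and MHC scores by arm.

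**A mixed version.** The 12-month rule within the same item IX looks at adherers in the intervention arm but at standard-care participants with no adherence condition.

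**What would settle it.** Section 9.3 lists regression models with confounder adjustment. It names no arm contrast and no analysis population. The Data Analysis paragraph at the end of Section 12 leaves the statistical analysis plan to be developed.

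**The concern.** Randomisation makes the two arms comparable. It does not make the adherers within them comparable. Adherence here is a choice made after allocation and reported by the participant at follow-up: of the follow-up questionnaires, 6.1 item VIII says "These measures will determine participants adherence to lifestyle recommendations of the Online intervention and standard course". Adhering also means something different in each arm, because each course gives its own advice, so the two groups of adherers may be selected to different degrees. No threshold for adherence is given. Section 6.1 defines a course completer by modules finished, which is a different thing and is tied to no analysis.

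If people whose quality of life is improving are more likely to keep to the advice, and one set of advice is harder to keep to, a course with no effect could appear to work or a real benefit could be hidden. Adjustment for unnamed confounders (9.3) cannot be relied on to restore the balance. With both formulations in the protocol, the choice between them could also be made after the results are seen.

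**Working it through.** **1. The plan's own sample size.** Section 9.1 gives 527 per arm, 80% power, a 5-point difference and 42% loss. Section 9.2 gives a Bonferroni correction without a numeric alpha, and no SD is stated, so 1054 cannot be reproduced outright. Assume two-sided alpha 0.05/2 = 0.025 (critical z 2.241) and SD 20:

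- n = 2 × (2.241 + 0.842)² × 20² / 5² = 304.2, so 305 per arm with data
- 305 / 0.58 = 526 randomised per arm, against 527 stated

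The working evaluable number is therefore 527 × 0.58 = 306 per arm, with SD about 20. Section 9.1 can also be read as 527 per arm with data, which implies SD 26.3. Neither reading allows for non-adherence among those retained.

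**2. Bias from comparing adherers (all inputs assumed).** Let adherers be the top fraction p of a latent normal score that has correlation r with quality-of-life change. Their mean change exceeds the whole arm's by SD × r × m(p), where m(p) = φ(c)/p and c is the normal quantile at 1 − p. This gives m(0.6) = 0.644 and m(0.8) = 0.350.

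- Bias = SD × r × [m(p₁) − m(p₂)]
- SE = SD × √(1/(n p₁) + 1/(n p₂))
- Type I error = 1 − Φ(2.241 − bias/SE) + Φ(−2.241 − bias/SE)

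Example with r = 0.2, 60% against 80%, n = 306 and SD 20: bias = 20 × 0.2 × (0.644 − 0.350) = 1.18; SE = 20 × √(1/183.6 + 1/244.8) = 1.95; type I error = 5.3%.

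| Adherence, intervention v control | Bias in points, r = 0.1 / 0.2 / 0.3 | Type I error, 306 per arm | Type I error, 527 per arm |
|---|---|---|---|
| 60% v 80% | +0.59 / +1.18 / +1.76 | 3.2 / 5.3 / 9.1% | 3.7 / 7.5 / 14.6% |
| 80% v 60% | −0.59 / −1.18 / −1.76 | 3.2 / 5.3 / 9.1% | 3.7 / 7.5 / 14.6% |
| 60% v 70% | +0.29 / +0.59 / +0.88 | 2.7 / 3.1 / 3.9% | 2.8 / 3.6 / 5.0% |
| 60% v 60% | 0 | 2.5% | 2.5% |

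Bias is at SD 20. At SD 26.3 the first row becomes 0.8 to 2.3 points. Type I error does not depend on the SD. A simulation of 20,000 trials per setting, allowing for the smaller variance among adherers, gave 3.1% and 9.6% for the first row at 306 per arm (r = 0.1 and 0.3).

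In the second row, a true 5-point gain in everyone would be seen as 5 − 0.59 = 4.41, 5 − 1.18 = 3.82 or 5 − 1.76 = 3.24 points. All are below the protocol's own 5-point threshold.

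**3. The 12-month rule.** Only the intervention side is restricted, so its mean change is raised by SD × r × m(p). At SD 20 that is 0.70, 1.40 or 2.10 points at 80% adherence, and 1.29, 2.58 or 3.86 points at 60%, against a 5-point trigger.

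**4. Power if only adherers gain 5 points (assumption; equal adherence in both arms).** With 5/SE = 3.083 at full n, all-randomised power is Φ(3.083p − 2.241) and adherers-only power is Φ(3.083√p − 2.241).

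| Adherence | All-randomised difference | Power, all randomised | Power, adherers only |
|---|---|---|---|
| 80% | 4.0 | 59% | 70% |
| 60% | 3.0 | 35% | 56% |
| 50% | 2.5 | 24% | 48% |

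**The case against.** The strongest reply is that the adherer wording of the objectives sits in the synopsis, while the body (hypothesis, endpoint definition, item IX, sample size) is by arm. On that view this is loose drafting and the intended analysis is clear enough. The lean towards a by-arm comparison is real. But the entry headed Primary Objectives says the opposite twice, the secondary objectives and study objective 2 repeat it, and nothing gives the by-arm text priority.

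Second, the illustration is assumed throughout, and no text says non-adherers will be dropped from a model. The key questions in 4.2 speak of levels of adherence, which suggests a graded analysis. The scale does depend on the adherence gap: with a 10-point gap (60% v 70% or 70% v 80%) at 306 per arm, type I error is only 2.7% to 4.2%. The figures at 527 evaluable per arm also sit badly with the 42% loss stated in 9.1. These points limit the size that can be claimed. They do not remove the contradiction.

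Third, the 12-month rule only triggers consideration of an amendment, and selection alone does not reach 5 points in the cases shown. That is correct. The rule matters here mainly as a third definition of who is compared.

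Fourth, the later statistical analysis plan could settle the matter. It could, but it is not in these documents and would inherit a contradictory objective. Missing data, the primary time point and standard-care participants' access to the intervention course after 12 months also need attention, but they are separate issues.

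**Conclusion.** The concern holds and should be corrected before analysis. The protocol gives two incompatible primary comparisons and no analysis population to choose between them, and the one labelled primary is not protected by randomisation. That conclusion rests on the text alone.

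Its numerical size is not known. Under the assumptions above (20-point adherence gap, correlation 0.1 to 0.3, SD 20, two-sided alpha 0.025, 306 evaluable per arm), bias is 0.6 to 1.8 points in either direction, and type I error is 3.2% to 9.1% instead of 2.5%. It shrinks with a smaller gap and vanishes when adherence and selection are equal in both arms. The case against the adherer comparison is bias; no claim is made that it loses power.

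**What to change.** Reword the primary objective, study objective 2 and the secondary objectives in the synopsis. State in 9.3 that the primary analysis is the between-arm difference in change in PHC and MHC among all randomised participants as assigned, regardless of course completion or adherence. Make adherence analyses secondary and exploratory, with a threshold defined before unblinding. Reconcile the adherer-based 12-month rule in 6.1 item IX with the by-arm text.

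Three optional clarifications would help: say in 8.3 that not completing the course is not study withdrawal; state the date from which follow-up is counted for non-completers; and word the causal aim in 5.2 and 6.1 as concerning the course, which is what is randomised.

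The change itself is wording only. Its downside is that the all-randomised effect, and the power to detect it, may be smaller than among adherers if non-adherers gain little (59%, 35% or 24% power at 80%, 60% or 50% adherence in the example above). If the sponsor expects that pattern, the sample size justification in 9.1 should say so.

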4. INTRODUCTION/BACKGROUND INFORMATION

4.1 LAY SUMMARY

The Multiple Sclerosis Online Course (MSOC), both the intervention and standard-care arms, was delivered as part of a feasibility study (MSOC - Feasibility study) in April to June 2021. In the MSOC – Feasibility study 31 participants from Australia, New Zealand, and the United States completed the MS Online course (n=15 intervention course and n=16 standard-care course). Examination of the acceptability and usability in the MSOC – Feasibility study was conducted via quantitative and qualitative analyses, with the results of these analyses currently in preparation for publication in a peer-reviewed journal.

In the proposed study, we plan to perform a randomised controlled trial (RCT) utilising the results from the MSOC – Feasibility study. That is, the MS Online course has been modified and redeveloped to test the effectiveness of the MS Online intervention and standard-care courses in a large international RCT (MSOC – RCT).

This RCT will analyse participant uptake and retention, adoption and adherence to lifestyle recommendations and health outcomes at baseline, and 6 months, 12 months, and 2.5 years after completing either the MS intervention or standard-care course. The significance of this study is that the RCT will test:

- 1) whether an MS Online educational intervention course, compared with a standard-care course, can change behaviour in people with MS and
- 2) whether an MS online educational intervention course, compared with standard-care course, leads to superior improved health outcomes in people with MS.

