4.2 INTRODUCTION

Although genetic factors are responsible for roughly 25% of the risk of multiple sclerosis (MS) onset, they play less of a part in disease progression. By contrast, disease progression and disability are associated or influenced by environmental factors including modifiable lifestyle behaviours. These risk factors include smoking, a diet high in saturated fat and low in omega-3 polyunsaturated fatty acids, lack of physical activity, inadequate vitamin D level, and stress. The amelioration of these risks is associated with a reduction in the chronic inflammatory state associated with MS (Fragoso, 2014), and subsequent improved health outcomes including improved mental and physical health quality of life (Hadgkiss, Jelinek, Weiland, et al., 2015; Jelinek et al., 2013; Marck et al., 2014), reduced relapse rate (D'Hooghe M, Nagels, Bissay, & De Keyser, 2010), depression risk (K. L. Taylor et al., 2014), clinically significant fatigue (T.J. Weiland et al., 2015; T. J. Weiland et al., 2015), and less disability and symptom burden (Fitzgerald et al., 2018; Jelinek et al., 2016). Lifestyle modification of these risk factors represents an effective, low cost and low risk intervention in MS.

Studies of a lifestyle modification programs for MS including evidence-based recommendations regarding diet, exercise, stress management, sun exposure, and vitamin D delivered via intensive face-to-face residential workshops. These workshops have demonstrated 11.3% and 19.5% improvement in overall quality of life at one and 5-year time-points post workshop, respectively, compared to baseline measures (Hadgkiss et al., 2013), and that behaviour change was feasible and sustainable (Marck et al., 2018). However face-to-face interventions are resource intensive and present potential barriers to participation for people with MS, including geographical, financial and disease specific factors such as fatigue and mobility. The COVID-19 pandemic has highlighted the highly unpredictable ability to travel and presented further MS specific challenges relating to potential immunosuppression and subsequent vulnerability of participants in face-to-face education.

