6. STUDY DESIGN

6.1 STUDY TYPE & DESIGN & SCHEDULE

1. Study Type: Clinical trial

Randomised controlled trial, involving:

- a. Epidemiological analysis of quantitative data
- b. Qualitative analysis of semi-structured interviews

2. Study Design (refer to Table 1)

- I. This is a single-site study that will be conducted at the Neuroepidemiology Unit in the Centre for Epidemiology and Biostatistics, Melbourne School of Population and Global Health at The University of Melbourne, involving online recruitment of participants with MS from Australia, New Zealand, USA, UK and Canada. The decision was made to make this a single-site study to guarantee that all data collected from participants (both personal participant data and responses to self-reported questionnaires) will be safely and securely stored in one location (on the University of Melbourne server).
- II. For participant recruitment, details of the RCT will be published on MS society websites and social media sites throughout Australia, New Zealand, USA, UK and Canada seeking interested people with MS to participate in the MSOC - RCT.
- III. Interested participants (people with relapsing-remitting MS) will be asked to click on a link on the notice advertising the MSOC - RCT which will direct them to 7 eligibility questions related to: (1) their age; (2) the type of MS they were diagnosed with; (3) the year they were diagnosed with MS (4,5) whether they follow a MS-specific diet and if so, the diet they follow (6,7) whether they follow a MS-specific program and if so, the program they follow.

- IV. Participants with MS over the age of 18 fulfilling inclusion and exclusion criteria from Australia, New Zealand, USA, UK, Canada and other countries who read, write and speak English will be invited to participate in the study. Note, the recruitment period will be up to two months from the date of the first participant recruitment or earlier, if the required number of eligible participants have been recruited.

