6.3 RANDOMISATION

Allocation

Sequence Generation

Participants will be randomly assigned to either control or intervention group with a 1:1 allocation as per a computer-generated simple randomisation program such as <https://www.randomizer.org/>.

Implementation

All patients who: 1. fulfil the study inclusion and exclusion criteria 2. give consent for participation in the study, and 3. complete the baseline assessment questionnaire will be randomised to either the intervention or standard-care arm of the study before being provided with a link to access to the MS Online course.

An assigned study investigator will be responsible for allocating participants to either the intervention or standard-care arm.

Participants will be blinded to the nature of the other study arm. That is, there will be no identifying information in the MS Online course and participants will be notified that they are enrolled in a “MS Online Education Course”. Participants will be allocated to the intervention or standard-care arm at a 1:1 ratio using simple randomization.

Research staff (including those researchers performing statistical analyses) will be blinded to the group allocation. Only the researcher responsible for allocating participants to either the intervention or standard-care arm and the data manager will have access to participant allocation information. The same researcher will be responsible for inviting participants to be involved in the qualitative study. In the event this researcher leaves the study, an external researcher will take over this position.

Group allocation information will be concealed from study participants.

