7.3 EXCLUSION CRITERIA

Exclusion criteria of participants include:

1. Experiencing any serious co-morbid chronic illness or neurological illness/injury other than MS that would threaten regular participation or significantly affect the outcome measures in

its own right, such as motor neurone disease or stroke, as determined by the study investigators;

2. Currently participating in another study ~~or self-management program involving modification of lifestyle.~~

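### Eligibility looks only at current participation, so MSOC-Feasibility participants and the advisers who co-designed the courses can be randomised; the effect is small and cheap to remove.

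*Combined protocol and SAP*

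**What the plan says.** - **Exclusion criterion 2.** The synopsis excludes those "Currently participating in another study or self-management program involving modification of lifestyle". Section 7.3 prints the same criterion with its second half struck through (the tildes mark the strike-through): "Currently participating in another study ~~or self-management program involving modification of lifestyle". Both open with the word for present participation. The inclusion criteria in Section 7.2 do not mention past exposure.
- **Screening.** Of the seven questions in Sections 6.1 (item III) and 7.1, four concern diet and programme, and these are in the present tense, for example "whether they follow a MS-specific program and if so, the program they follow". Table 1 repeats the diet and programme items at baseline and at each follow-up. It has no item on a past course, workshop or advisory role.
- **People with earlier exposure.** Section 4.1 reports that "31 participants from Australia, New Zealand, and the United States completed the MS Online course" between April and June 2021, 15 in the intervention course and 16 in the standard-care course. The RCT recruits in all three countries (Section 6.1). The synopsis adds: "A consumer advisory group comprising of 6-8 people with MS in a series of focus groups was involved in the co-design" of both courses. Section 12 puts that group at up to 6.
- **Blinding.** Section 6.3 states: "Participants will be blinded to the nature of the other study arm".
- **Outcomes.** The health and lifestyle outcomes in Section 5.3 are self-reported, including the co-primary changes in PHC and MHC.

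**The concern.** Participant blinding here depends on people not knowing how the two courses differ. An adviser who worked on both knows. Someone who took the intervention course in 2021 and is now allocated to standard care would probably notice that the content is different. With self-reported outcomes, that knowledge can affect the answers.

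There is also a dilution problem. A person who has already received the intervention content has less left to gain from it, and if allocated to control is not an unexposed control. Either way that person adds little to the between-arm difference in change from baseline. Because past exposure is neither excluded nor recorded, the analysis could not identify these participants afterwards.

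**Working it through.** **1. The plan's own sample size.** Section 9.1 gives 1054 participants (527 per arm), 80% power, a 5-point difference and 42% loss to follow-up at 12 months. Section 9.2 says Bonferroni was used for two outcomes. Neither section gives an SD or a numeric alpha. I assume two-sided alpha 0.05/2 = 0.025 and try SD 20:

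- n per arm = 2 × [20 × (2.2414 + 0.8416)/5]² = 304.2, so 305 evaluable.
- Inflated for loss: 305/(1 − 0.42) = 525.9, so 526 per arm, or 1052 in total.

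This is within one per arm of the stated 527, which leaves 527 × 0.58 ≈ 306 evaluable. The fit is not unique: SD 22 at alpha 0.05 gives 525 per arm, and SD 26.3 at alpha 0.025 fits if 527 is read as the evaluable number. The stated figure is plausible but cannot be verified.

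**2. How many people can be counted.**

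- All completers plus the larger adviser count: 31 + 8 = 39; 39/1054 = 3.7%.
- Those who had the intervention content: 15 + 8 = 23; 23/1054 = 2.2%. With Section 12's figure of up to 6 advisers it is 21, or 2.0%.

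The 16 standard-care completers belong in the blinding count. They do not belong in the dilution count in the same way, because the intervention content would be new to them if they were randomised to it.

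**3. Dilution, worst case.** Suppose all of them enrol, are retained like everyone else, and show zero between-arm difference. With exposed share f, the expected difference is 5(1 − f). The standard error is 20 × √(2/306) = 1.617, and power = Φ(difference/1.617 − 2.2414).

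| Exposed | f | Difference | Power |
|---|---|---|---|
| 0 | 0 | 5.00 | 80.3% |
| 23 | 2.2% | 4.89 | 78.3% |
| 39 | 3.7% | 4.81 | 76.9% |

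Using SD 26.3 with 527 evaluable per arm gives 80.1%, 78.2% and 76.7%, so the result does not depend on which reading of the sample size is right.

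**4. Limit of the count.** Section 4.1 counts completers. The documents do not say how many people, if any, began a feasibility course without finishing it, so 39 is the most that can be counted from the text.

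**The case against.** Nothing in the documents says that any of these people will apply. Exposure precedes randomisation and is balanced between arms in expectation, so the main effect is dilution, not a systematic difference between arms. Section 4.1 says the course was modified and redeveloped after the feasibility study, so recognition is likely but not certain. A feasibility participant saw one course, not both. All of this stands, and it is why the size is small.

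Two stronger readings are tempting, and the documents do not support either.

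- **That blinding is defeated for the trial.** At most 3.7% of the sample can be counted as able to recognise an arm. That is a local failure of blinding.
- **That past attendees of the face-to-face workshops cause a large loss.** Section 4.2 says "These workshops have demonstrated 11.3% and 19.5% improvement in overall quality of life at one and 5-year time-points post workshop", so a lasting effect in attendees is plausible. But the documents give no number of attendees, and Section 4.3 places the workshops in Australia while recruitment covers five named countries and social media worldwide. Attendees who still follow a programme or diet should say so at screening, although no rule states which answers exclude. Attendees who have lapsed have room to change again. Any figure for power lost through this group would be invented. Admitting them is also defensible in an effectiveness trial of a course meant for people with MS generally.

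**Conclusion.** The gap is real but small. As written, both versions of criterion 2 and the screening questions let feasibility participants and course advisers be randomised. For these people the blinding in Section 6.3 is unlikely to hold, and those who already had the intervention content pull the difference towards zero. The worst case costs about 2 to 3 percentage points of power. That assumes full enrolment of these people, zero contrast among them, SD 20, two-sided alpha 0.025 and 306 evaluable per arm. The likely cost is lower.

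The trial's validity is not in question. The change is worth making because the groups are known and barring them costs almost nothing.

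The two statements of criterion 2 must be reconciled at the same time. If the strike-through in Section 7.3 is intended, current users of lifestyle programmes are eligible under that section and ineligible under the synopsis. A past-exposure rule cannot be placed sensibly until that is settled.

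**What to change.** 1. Reconcile exclusion criterion 2 between the synopsis and Section 7.3, so that one text governs whether current users of lifestyle programmes may enter.
2. In both places add an exclusion for previous participation in MSOC-Feasibility (either course, finished or not) or in the advisory or focus groups for the course. Add one matching yes/no question to the screening set in Sections 6.1 and 7.1.
3. Do not exclude past workshop attendees. Add one baseline question on past attendance to Table 1, and pre-specify in Section 9.3 a sensitivity analysis of PHC and MHC without those who answer yes. Because the answer is given before randomisation, dropping them keeps the comparison between randomised groups.

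Cost: a few willing applicants are lost and two short questions are added, one at screening and one at baseline. The planned 1054 does not change.
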